6.3 Withdrawal and escape criteria

6.3.1 Withdrawal criteria

Subjects are free to withdraw from the study at any time, without prejudice to their continued care.

Subjects should be withdrawn from the study if any of the following events occur:

1. Subject develops an illness that would interfere with his/her continued participation.
2. Subject is noncompliant with the study procedures or medications in the opinion of the Investigator.
3. Subject takes prohibited concomitant medications as defined in this protocol.
4. Subject withdraws his/her consent.
5. There is confirmation of a pregnancy during the study, as evidenced by a positive pregnancy test.
6. The Sponsor or a regulatory agency requests withdrawal of the subject.
7. Subject's subsequent TB test was confirmed positive or any further evidence is suggestive of potential TB infection (eg, exposure) and further examinations result in a diagnosis of active TB, or in case of LTB no prophylactic treatment was initiated. Refer to [Section 12.7.3](#) for further details and instructions.

Once withdrawn from study treatment, subjects must return for the WD Visit, complete all WD assessments, and complete a final SFU Visit 10 weeks after the last dose of study medication.

Investigators should attempt to obtain information on subjects in the case of withdrawal or discontinuation. For subjects considered as lost to follow-up, the Investigator should make an effort (at least 1 phone call and 1 written message to the subject), and document his/her effort (date and summary of the phone call and copy of the written message in the source documents), to complete the final evaluation. All results of these evaluations and observations, together with a narrative description of the reason(s) for removing the subject, must be recorded in the source documents. The Case Report form must document the primary reason for withdrawal or discontinuation.

Investigators should contact the Medical Monitor, whenever possible, to discuss the withdrawal of a subject in advance.

Subjects withdrawn from the study will not be replaced.

6.3.2 Escape treatment

Subjects receiving placebo or half-dose CZP (200mg Q4W) who experience a flare during the Double-Blind Period will escape to full-dose treatment (CZP 200mg Q2W) until the end of that period or for at least 12 weeks, whichever is longer. The escapers need to come back to the site at the timepoint of the escape (Week 0), 2 and 4 weeks after escape (Weeks 2 and 4), and every 12 weeks thereafter until the originally scheduled Week 96.

Subjects escaping from placebo to full-dose CZP (200mg Q2W) will receive a loading dose of CZP (400mg Q2W; 2 injections) at the 3 consecutive visits after the flare. Subjects escaping

from half-dose CZP to full-dose CZP will receive a loading dose of CZP 200mg Q2W at the 3 consecutive visits after the flare. In order to maintain the blind, subjects escaping from half-dose CZP to full-dose CZP will receive a placebo administration and a CZP 200mg administration (a total of 2 injections) at these 3 visits ([Figure 7.1](#)).

Subjects randomized to the CZP full-dose (200mg Q2W) treatment during the Double-Blind Period who qualify for escape will remain on their current treatment allocation. As with subjects escaping from half-dose CZP to full-dose CZP, these subjects will receive a placebo and CZP 200mg injection (a total of 2 injections) at the 3 visits after the flare in order to maintain the blind to the randomized treatment.

After the loading dose (200mg Q2W or 400mg Q2W), all escaped subjects will continue full-dose CZP treatment in an open-label fashion.

The definition of flare is provided in [Section 3](#).

At the Investigator's discretion, the subject may be withdrawn from the study at any time (eg, to receive alternative treatment for the disease).

7 STUDY TREATMENT(S)

7.1 Description of investigational medicinal product(s)

Investigational medicinal products will be supplied under the responsibility of the UCB Clinical Supply Unit. The frequency at which the IMP will be supplied to each individual center will be adapted to the recruitment capacity of that center and to the expiry date of the IMP and will be managed by the IXRS.

Drug supplies will consist of the following:

Certolizumab pegol is supplied as a sterile, clear, and colorless to slightly yellow liquid solution with a pH of approximately 4.7 in 1mL single use glass prefilled syringe (PFS) with a 25G ½ inch thin wall needle for sc administration. Each syringe contains an extractable volume of 1mL at a concentration of 200mg/mL of CZP in 10mM sodium acetate buffer and 125mM sodium chloride as a tonicity agent.

Placebo is supplied in a PFS with a 25G ½ inch thin-wall needle, containing an injectable volume of 1mL 0.9% saline for single use.

Due to the difference in presentation and viscosity between CZP and placebo, special precautions will be taken in order to ensure maintained blinding of the study (unblinded/blinded site personnel and monitors).

7.2 Treatment(s) to be administered

Treatments to be administered are as described in [Section 5.1](#).

7.2.1 Treatment administration

Part A

A Pharmacy Manual will be provided to each site containing instructions regarding drug preparation and dosing. The administration schedule is described in [Section 5.1.1](#).

Study medication will be given sc by dedicated and adequately trained site personnel or the subject may start self-administering from Week 6 after training at Week 2 and Week 4.

Suitable areas for administrations are the lateral abdominal wall and upper outer thigh. During each dosing visit, if 2 injections are being administered (ie, loading dose CZP 400mg as 2 injections of 200mg each) each of the 2 injections should be administered at a separate injection site.

Study medication should be administered with a minimum of 10 days between the CZP 200mg Q2W administrations. Each deviation less than the minimum timeframe must be discussed immediately with the Medical Monitor for safety purposes.

Part B

A Pharmacy Manual will be provided to each site containing instructions regarding drug preparation and dosing. The administration schedule is described in [Section 5.1.2](#).

Injections will be given sc by dedicated, unblinded and adequately trained site personnel. Suitable areas for administrations are the lateral abdominal wall and upper outer thigh.

Injections should be administered with a minimum of 10 days between the CZP 200mg Q2W administrations. Each deviation less than the minimum timeframe must be discussed immediately with the Medical Monitor for safety purposes.

7.3 Packaging

For Part A and B, CZP and placebo are packaged and labeled according to Good Manufacturing Practice guidelines and applicable laws or regulations. They are suitably packaged in such a way as to protect the IMP from deterioration during transport and storage.

7.4 Labeling

Clinical drug supplies will be labeled in accordance with the current International Conference on Harmonisation (ICH) guidelines on Good Clinical Practice (GCP) and Good Manufacturing Practice and will include any locally required statements. If necessary, labels will be adapted to the size of IMP package, and translated into the local language. Details on the labeling of the IMP will be provided in the Pharmacy Manual.

7.5 Handling and storage requirements

The Investigator (or designee) is responsible for the safe and proper storage of IMP at the site. The IMP stored by the Investigator is to be kept in a secured area with limited access. The IMP containers should be stored at 2 to 8°C and protected from light.

Appropriate storage conditions must be ensured by a controlled temperature and by completing a temperature log in accordance with local requirements on a regular basis (eg, once a week) showing minimum and maximum temperatures reached over the recorded time interval.

In case an out of range temperature is noted, it must be immediately communicated to the Sponsor's designee in accordance with the Pharmacy Manual.

The Investigator (or designee) will instruct the subject to store the IMP following the instructions on the label.

Detailed information on handling and storage of IMP will be given in the Pharmacy Manual.

7.6 Drug accountability

A Drug Accountability form will be used to record IMP dispensing and return information on a by-subject basis and will serve as source documentation during the course of the study. Details of any IMP lost (due to breakage or wastage), not used, disposed of at the study site, or returned to the Sponsor or designee must also be recorded on the appropriate forms. All supplies and pharmacy documentation must be made available throughout the study for UCB (or designee) to review.

The Investigator (or designee) is responsible for retaining all used, unused, and partially used containers of IMP until returned or destroyed.

The Investigator may assign some of the Investigator's duties for drug accountability at the study site to an appropriate pharmacist/designee.

The Investigator must ensure that the IMP is used only in accordance with the protocol.

Periodically, and/or after completion of the clinical phase of the study, all used (including empty containers) and unused IMP containers must be reconciled and returned to UCB (or designee), preferably in their original package. Investigational medicinal product intended for the study cannot be used for any other purpose than that described in this protocol.

All study medication documentation (eg, shipping receipts, drug accountability logs, IXRS randomization materials) must be maintained and accessed by unblinded, trained site personnel only. Designated, unblinded site personnel must be appropriately trained and licensed (per country guidelines) to administer study drug. Each site will be required to have a written blinding plan in place signed by the Principal Investigator, which will detail the site's steps for ensuring that the double blind nature of the study is maintained from Week 48 to Week 96.

7.7 Procedures for monitoring subject compliance

At each visit after IMP is dispensed, subjects must return all unused IMP and empty IMP containers. Drug accountability must be done in the subject's presence in order to obtain explanations regarding discrepancies in compliance with the dosing regimen. Drug accountability must be recorded on the Drug Accountability form.

Part A (Open-Label Period: Week 0 [Baseline] to Week 48)

If a subject is found to be persistently noncompliant (3 or more missed doses in total over 48 weeks), the Sponsor, in conjunction with the Investigator, will make a decision as to whether the subject should be withdrawn from the study. Doses of IMP that were missed due to a reasonable interfering AE that does not allow administration of an anti-TNF due to safety reasons, will not be considered for the evaluation of subject compliance. Evaluation of the reasonability of the AE must be discussed immediately with the Medical Monitor.

Part B (Double-Blind Period: Week 48 to Week 96)

If a subject is found to be persistently noncompliant (3 or more missed doses over any period of 48 weeks), the Sponsor, in conjunction with the Investigator, will make a decision as to whether the subject should be withdrawn from the study. Doses of IMP that were missed due to a reasonable interfering AE that does not allow administration of an anti-TNF due to safety reasons, will not be considered for the evaluation of subject compliance. Evaluation of the reasonability of the AE must be discussed immediately with the Medical Monitor.

7.8 Concomitant medication(s)/treatment(s)

For any subject taking any medication, including over the counter products, nutraceutical products, or herbal medications at Screening or at any time during the course of the study, an accurate record must be kept in the clinic chart (source documentation) and the eCRF. This record should include the name of the drug, the dose, the date(s) of administration, and the indication for use.

7.8.1 Permitted concomitant treatments (medications and therapies)

The following concomitant medications/treatments are permitted during the study, from Baseline onward, with restrictions as specified:

- NSAIDs/cyclooxygenase 2 (COX-2) inhibitors: doses should be stable throughout the study and ad hoc as needed (prn) inhibitors should not be used 24 hours prior to any post-Screening study visit. No change in dose or dose regimen is allowed during the study except for reasons of safety, where the NSAIDs/COX-2 inhibitors dose may be decreased or discontinued. NSAID dose may be down-titrated at Investigator discretion. The reduction in NSAID dose if clinically indicated is permitted at the discretion of the Investigator until Week 28, however after that timepoint the NSAID treatment should remain stable as much as possible.
- Stable doses of analgesics (including, but not limited to acetaminophen, paracetamol, NSAIDs, opiates or combinations) will be permitted except that ad hoc (prn) usage is prohibited within the 14 days prior to Baseline or 24 hours prior to any post-Screening assessments.
- Corticosteroids (see [Section 7.8.2](#) for prohibited corticosteroids):
 - Oral chronic stable doses are allowed as long as the maximum daily total prednisone equivalent dose is ≤ 10 mg. Oral corticosteroid tapers of less than 14 days used to treat other indications (asthma exacerbation, contact dermatitis, etc.) are allowed as long the maximum daily dose is ≤ 20 mg. The taper must end 1 week before a study visit.
 - Intra-articular (ia): ia administrations of corticosteroids are permissible in peripheral joints; however, after an ia injection the joint will no longer be evaluated for data regarding swollen and tender joints.
 - Intravenous (iv): iv administration of corticosteroid will be permitted for the purposes of stress dosing for a surgical procedure under general or spinal anesthesia. Furthermore, iv administration of corticosteroids may be used during the study for acute illnesses as long as the dose is not given within 1 week prior to Week 12, Week 24, Week 48, or Week 96, and the underlying disease does not present a contraindication to the subject remaining in the study. Indications might include dermatitis, gastroenteritis, asthma exacerbation, and pneumonia.
- Slow-acting anti-rheumatic drugs (SAARDs) (only SSZ and/or HCQ and/or MTX and/or azathioprine [AZA] and/or leflunomide [LFN]: maximum SSZ ≤ 3 g daily; HCQ ≤ 400 mg daily; MTX ≤ 25 mg weekly; AZA ≤ 150 mg daily; LFN ≤ 20 mg daily) are allowed. No change in dose or dose regimen is allowed during the study except for reasons of intolerance, where the SAARDs dose may be reduced or discontinued. No change is permitted in the route of administration for MTX (sc, or oral) during the study.

- Osteoporosis medications (eg, risedronate, alendronate, ibandronate, denosumab, cathepsin K inhibitor, cinacalcet, calcitonin) with the exception of iv bisphosphonates are allowed without restriction.

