4.1.3 Other efficacy variables

4.1.3.1 Other efficacy variables for subjects entering Part A

The following other efficacy variables for subjects entering Part A will be evaluated at all scheduled study visits where the assessment is performed through Week 48.

- ASAS20, ASAS40, ASAS5/6, and ASAS PR response
- BASDAI50 response
- Change from Baseline in ASDAS, BASDAI, and BASMI
- ASDAS disease activity (ASDAS-ID, ASDAS-MD, ASDAS-HD, and ASDAS-vHD) and clinical improvement (ASDAS-CII, ASDAS-MI)
- Change from Baseline in sacroiliac SPARCC and ASspIMRI-a in the Berlin modification scores
- Change from Baseline in all individual ASAS core components
 - Patient's Global Assessment of Disease Activity (PtGADA)
 - Total spinal pain (Numeric Rating Scale [NRS])
 - BASFI
 - Average of Questions 5 and 6 of the BASDAI concerning morning stiffness
- Change from Baseline in nocturnal spinal pain (NRS)
- Change from Baseline in spinal mobility, as assessed by occiput to wall distance
- Change from Baseline in spinal mobility as assessed by chest expansion
- Change from Baseline in PhGADA

- Change from Baseline in Fatigue (NRS) (from BASDAI)
- Change from Baseline in CRP
- Change from Baseline in ASQoL
- Change from Baseline in Work Productivity Survey (WPS)
- Health status as assessed by the EuroQoL Health Status Questionnaire 5 dimensions (EQ-5D): domains, visual analog scale (VAS) actual score and change from Baseline in VAS score
- Change from Baseline in Maastricht Ankylosis Spondylitis Enthesitis Score (MASES)
- Change from Baseline in swollen and tender joint counts (44 joint count)
- Number of uveitis flares
- Number of IBD exacerbations
- Change from Baseline in fecal calprotectin
- Change from Baseline in serum calprotectin
- Change from Baseline in the IBD-Q
- Correlation between fecal calprotectin, serum calprotectin, IBD-Q, and CRP
- Number of psoriasis exacerbations (in subjects with concurrent psoriasis)
- Change from Baseline in all Short-Form 36-Item Health Survey (SF-36) domains, SF-36 Physical Component Summary (PCS), and SF-36 Mental Component Summary (MCS)
- Resources utilization: concomitant medical procedures, healthcare provider consultations not foreseen by the protocol, hospitalizations/emergency room visits

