NSAIDs (including cyclooxygenase 2 [COX 2] inhibitors)	Up to maximum approved dose regimen	Any change in stable dose regimen is excluded in the 14 days prior to the Baseline Visit.	Any ad hoc (prn) use of NSAIDs is not permitted within 24 hours prior to any postscreening visit. NSAID dose can be down-titrated at Investigator discretion, if clinically indicated, until Week 28, after which NSAID treatment should remain as stable as possible. NSAID dose should be stable until Week 96 (if subjects have to decrease or stop taking medication due to safety reasons, they may reduce their dose and continue in the study).
Oral corticosteroids	Maximum allowed \leq 10mg daily total prednisone equivalent ^a	Any change in stable dose used for axSpA in the 28 days prior to the Baseline Visit.	A change in the dose is not allowed until Week 96. Oral corticosteroid tapers of less than 14 days used to treat other indication (asthma exacerbation, contact dermatitis, etc) are allowed as long as the maximum daily dose is \leq 20mg. The taper must end at least 1 week before study visit.
Intramuscular (im) corticosteroids	Any dose	Use in the 28 days prior to the Baseline Visit.	Intramuscular corticosteroids must not be used during the study.

Table 6.1: Concomitant Medications (Prior to Baseline and Study Visits)

Drug class	Dose	Exclusion criteria	Study Visits
Intra-articular (ia) corticosteroids	Up to maximum approved dose	Use in the 28 days prior to the Baseline Visit.	SIJ ia corticosteroid injections are not allowed during the study. Peripheral joint injections are permitted.
Intravenous (iv) corticosteroids	Up to maximum approved dose	Use in the 28 days prior to the baseline Visit.	iv doses of corticosteroids may be used during the study for acute illnesses as long as the dose is not given within 1 week prior to Week 12, Week 24, Week 48, or Week 96 and the underlying disease does not present a contraindication to the subject remaining in the study. Indications might include dermatitis, gastroenteritis, asthma exacerbation, and pneumonia.
Hyaluronic acid (ia)	Any dose	Use in the 28 days prior to the Baseline Visit.	After Baseline ia injection of hyaluronic acid may be used in the knee.

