9.2.6 Swollen and tender joint counts (44 joints evaluation)

The following 44 joints are to be examined for swelling and tenderness by the Principal Investigator, another delegated physician, or an appropriately qualified medical professional (based on local requirements) who has had documented training on how to perform these assessments correctly. Preferably the same assessor should evaluate the subject at each arthritis assessment.

- Upper body (4) – bilateral sternoclavicular, and acromioclavicular joints.
- Upper extremity (26) – bilateral shoulders, elbows, wrists (includes radiocarpal, carpal and carpometacarpal bones considered as a single unit), metacarpophalangeals (MCPs) I, II, III, IV, and V, and thumb interphalangeals (IPs), and proximal IPs (PIPs) II, III, IV, and V).
- Lower extremity (14) – bilateral knees, ankles, and metatarsophalangeals (I, II, III, IV, and V).

The assessment for swelling and tenderness is made on 44 joints from the above list. Artificial and ankylosed joints are excluded from swelling and tenderness assessments.

The assessments per visit are described in the schedule of study assessments [Table 5.1](#).

Table 9.1: Swelling and tenderness grading

Grade	Swelling response (44)	Tenderness response (44)
0	None	None
1	Swelling present	Tenderness present

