14.3.3.2 Part B

Treatment group comparisons for both CZP groups vs placebo will be performed based on the change from Baseline in other selected efficacy variables. These analyses will be performed using an ANCOVA model with variables of Baseline score, treatment group, region, and mNY criteria (yes/no) in the model. The treatment differences and corresponding 95% CIs will be calculated based on the adjusted means. Missing values will be imputed using LOCF. This analysis approach will be used for the following variables:

- Total spinal pain
- Nocturnal spinal pain
- PtGADA
- Morning stiffness (BASDAI 5 and 6)
- SF-36 PCS, MCS, and physical function domain
- Fatigue NRS
- ASQoL

Such analyses will also be done for the following continuous variables: ASDAS, BASDAI, BASFI, and BASMI will be analyzed using a MMRM similar to the one specified in [Section 14.3.2.2](#) at timepoints not covered in the secondary efficacy analyses. Additionally, ASDAS-MI, ASDAS-CH, ASAS, and BASDAI50 response variables will be analyzed using a logistic regression model similar to the one specified for binary response variables in [Section 14.3.2.2](#) at timepoints not covered in the secondary efficacy analyses.

These comparisons are not part of the multiplicity-controlled testing procedure described in [Section 14.2](#). The p-values reported for these analyses will not be adjusted for multiplicity and will be considered nominal. Exploratory statistical comparisons will also be performed for WPS scores using the nonparametric bootstrap-t method. This will be explained in greater detail in the SAP.

All other efficacy variables will be summarized descriptively by visit and treatment group using observed case and imputed data based on the RS.

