14.6 Handling of dropouts or missing data

For the primary efficacy variable (percentage of subjects in Part B who do not experience a flare), an approach based on the principles of NRI will be used to impute missing values. Specifically, if a subject withdraws from Part B at any point, they will be considered as having not responded to treatment. Therefore, they will be assumed to have experienced a flare during Part B for analysis purposes. If a subject has an intermittent missing ASDAS score (ie, a missing value at 1 visit but nonmissing values at the previous and subsequent visit), then the missing value will be ignored and flare will be based on the 2 available values. If the ASDAS score is missing at 2 or more consecutive visits, then the subject will be treated as having experienced a flare (even if ASDAS scores are available after the missed visits).

For the time to flare endpoint, the rules as described above for the primary endpoint will be applied to account for missing data when determining whether or not a subject experienced a flare. Subjects who discontinue the study without meeting the criteria for flare will be censored

at the time of their last study visit. Subjects who complete the study without meeting the criteria for flare will be censored at their Week 96 visit.

Selected continuous secondary efficacy variables will be analyzed using MMRM methods (see [Section 14.3.2.2](#) for details). Missing data for binary response secondary efficacy variables will be handled using NRI. Secondary variables related to MRI will be analyzed based on the observed case data.

In general, other efficacy variables will be summarized as both observed case and with imputation (NRI for binary response variables and LOCF for continuous variables), unless otherwise specified. Nonresponse imputation is implemented by treating missing data for binary response variables as a nonresponse. The LOCF summaries will impute missing continuous data using the last post-Baseline nonmissing result. In the event that a subject has no post-Baseline data for a given continuous variable, no imputation will be performed.

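### Section 7.8.1 drops a steroid-injected joint from later swollen and tender counts, Section 9.2.6 does not mention this, and nothing adjusts the Baseline count

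*Protocol*

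**What the plan says.** Protocol Table 6.1 (Section 6.2) restricts intra-articular corticosteroid before entry: "Use in the 28 days prior to the Baseline Visit" is exclusionary. During the study, sacroiliac injections are ruled out, but "Peripheral joint injections are permitted", with no limit on number or timing. Section 7.8.1 repeats the permission and adds the consequence for the joint data: "after an ia injection the joint will no longer be evaluated for data regarding swollen and tender joints".

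Section 9.2.6 describes the assessment itself: "The assessment for swelling and tenderness is made on 44 joints from the above list". Its only exclusion is this: "Artificial and ankylosed joints are excluded from swelling and tenderness assessments". Table 9.1 grades each joint 0 or 1 for swelling and for tenderness. It has no code for a joint that could not be evaluated.

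Change from Baseline in the 44-joint counts is an other efficacy variable in Part A (Section 4.1.3.1) and Part B (Section 4.1.3.2). It is absent from the list for subjects who flare (Section 4.1.3.3) and from their schedule (Table 5.2). Section 14.3.3.2 does not include it among the variables compared by ANCOVA, MMRM or logistic regression, so it falls under the residual sentence: "All other efficacy variables will be summarized descriptively by visit and treatment group using observed case and imputed data based on the RS".

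**The concern.** A joint injected during the study would normally have been examined at Baseline, because recent injections are excluded. From the injection on, Section 7.8.1 removes it from the joint data. Change from Baseline then compares a Baseline count that includes the joint with later counts that do not.

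The loss is unlikely to be random, since a joint chosen for a steroid injection is plausibly an active one. Dropping it tends to make the later count look better, and in open-label Part A there is no comparator to show this. In Part B the arms would be affected differently only if injection rates differed between them.

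The two sections also give sites different instructions. A site working from Section 9.2.6 would grade an injected joint, whereas a site working from Section 7.8.1 would not.

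**Working it through.** **The plan's own figures.** The protocol states none for joint counts. Its power figures (Section 14.8: 98% and 94%, with 70 per arm and no-flare rates of 80%, 75% and 45%) concern the primary endpoint. A continuity-corrected normal approximation gives 98.9% and 94.1%. Joint counts do not enter that calculation.

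**Inputs.** From the protocol: 44 joints, each graded 0 or 1, and an injected joint not evaluated afterwards. Assumed for illustration, because the protocol gives no counts: B joints active at Baseline, k joints later injected, and r other joints still active at the later visit.

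**Formulae for change from Baseline, injected joints active at Baseline:**
- injected joints retained as active: (r + k) − B
- plain sum, joints dropped later but kept at Baseline: r − B
- prorated to 44: r × 44/(44 − k) − B
- joints removed from both ends: r − (B − k)

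| B | k | r | Retained | Plain sum | Prorated | Removed from both |
|---|---|---|---|---|---|---|
| 1 | 1 | 0 | 0 | −1 | 0 × 44/43 − 1 = −1.00 | 0 |
| 2 | 1 | 1 | 0 | −1 | 1 × 44/43 − 2 = −0.98 | 0 |
| 4 | 1 | 3 | 0 | −1 | 3 × 44/43 − 4 = −0.93 | 0 |
| 6 | 2 | 4 | 0 | −2 | 4 × 44/42 − 6 = −1.81 | 0 |

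Proration recovers little, and nothing when the injected joint was the only active one.

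**Injected joint inactive at Baseline.** Take 3 other joints active at both visits and 1 newly active joint that is injected. Retaining it gives 4 − 3 = +1. The plain sum gives 3 − 3 = 0, proration gives 3 × 44/43 − 3 = +0.07, and removal from both ends gives 0. Here a worsening is missed.

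**LOCF.** Section 14.6 says: "The LOCF summaries will impute missing continuous data using the last post-Baseline nonmissing result". That rule works on the variable, not on the single joint. A count formed from 43 joints is not missing, so LOCF would not act unless one unevaluated joint made the whole count missing, which the protocol does not say.

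**Group mean.** Bias = share of subjects with one Baseline-active joint injected × 1 joint. The protocol gives no injection rate. If the share is 2% to 10% (assumption), the bias is 0.02 × 1 = 0.02 to 0.10 × 1 = 0.10 joints. If one Part B arm sat at 2% and another at 10%, the difference between them would shift by 0.10 − 0.02 = 0.08 joints.

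**The case against.** The strongest reply is that Section 7.8.1 makes the joint's data missing and does not score it 0. In Table 9.1 grade 0 means nothing was found on examination, so an unexamined joint has no grade. How a missing joint enters the count is the kind of derivation left to an SAP, and Section 14.3.3.1 refers to the SAP for details of the Part A other variables. Declining to read a joint after a local steroid is also reasonable, because the reading would reflect the steroid. This stands as far as it goes: the protocol does not fix a plain sum or proration, and removal from both ends would leave no false improvement.

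It does not dispose of the point. Sections 7.8.1 and 9.2.6 differ on what is collected at the visit, and no SAP can recover grades that were never taken. Section 7.8 requires the drug, dose, dates and indication of a concomitant treatment, but not which joint was injected.

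A reader might infer that an injected joint is scored as resolved, or that it is a joint in which study treatment failed. The documents support neither. The first follows only under particular derivations, and no indication for the injection is stated. Nor does every injected joint add a full joint of false improvement at every later visit, since that requires it to have been active at Baseline and to be counted as still active afterwards.

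Carrying forward the last scheduled grade would be a weak remedy. Section 8.3.1 places most joint counts 12 weeks apart, so that grade could be 0 for a joint that became active between visits.

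**Conclusion.** The point holds as a minor one. Section 7.8.1 makes an injected joint non-evaluable from the injection on, Section 9.2.6 does not reflect this, and nothing adjusts the Baseline count. Under a plain sum, each injected joint that was active at Baseline lowers the change score by 1.00 compared with counting it as still active. Under proration the net lowering in the examples is about 0.9 to 1.0 per injected joint. If the joint was inactive at Baseline, the consequence is an unseen worsening.

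The reach is limited. The variable is descriptive. The peripheral item in ASDAS is patient-reported (BASDAI question 3, Section 9.1.7), and the ASAS domains in Section 9.1.1 contain no joint count, so the flare endpoint, those responses and the sample size are unaffected. A reader might conclude that the rule flatters placebo and half-dose in Part B. That would need unequal injection rates, which the protocol does not give. Subjects who flare also have no scheduled joint counts on the escape schedule before their final assessment.

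**What to change.** - Reconcile Sections 7.8.1 and 9.2.6 so that both say the same about injected joints, with a cross-reference, and provide a way to mark such a joint in the grading.
- Record which joint was injected and its swollen and tender grade at the time of injection.
- In the count, let the joint keep that grade from then on. Count it as active if no grade was taken at injection.
- Add a sensitivity summary that removes the joint from both the Baseline and the later counts. This puts both ends on the same joints, but it cannot show a worsening in a joint that was inactive at Baseline, so it should not be the main derivation.

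The cost is one extra data field, a short derivation rule and slightly less favourable counts. Which injections are permitted does not change.
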